## 6.2 Primary endpoint analysis

### 6.2.1 Variable

The primary efficacy endpoint is the change from baseline to Week 4 of DB treatment in mean trough SiSBP measured by AOBPM.

Here 'mean trough' denotes the average of four AOBPM readings (from a Microlife® WatchBP Office device performing five readings; the first is excluded from the average which will be in the vendor's data transfer) taken at trough (i.e., before the morning intake of study treatment and standardized background antihypertensive therapy).

### 6.2.2 Intercurrent events and choice of estimand

There are two types of intercurrent events that may interfere with the analysis of the primary endpoint: premature discontinuation of DB treatment or the addition / dose increase of a diuretic. Use of rescue medication, although not allowed during the DB part, will be also considered as an intercurrent event.

All AOBPM measurements, irrespective of any intercurrent event(s), will be included in the main analysis, leading to a treatment policy strategy estimand in ICH terminology [ICH 2017b].

Based on the Phase 2 study in essential hypertension, AC-080A201, it is expected that 5% of subjects in the FAS will have a missing Week 4 AOBPM, mainly due to premature treatment discontinuation. In the main analysis [Section 6.2.3] missing data will not be imputed but will be handled by a mixed model assuming that the data are MAR. Sensitivity analyses will be performed, investigating the impact of deviations from MAR as well as considering a different estimand [Section 6.2.4].

### 6.2.3 Main analysis for the primary endpoint

The main analysis of the change from baseline to Week 4 (i.e., in the DB part) in mean trough SiSBP measured by AOBPM will be conducted on the FAS. The treatment groups in this analysis are aprocitentan 25 mg, aprocitentan 12.5 mg, and placebo. The first and second null hypotheses ( $H_{10}$  and  $H_{20}$ ) will be tested as described in Section 6.1.

Changes from baseline to post-baseline visits up to Week 4 in mean trough SiSBP will be analyzed using a mixed model with factors for treatment group, visit and treatment by visit interaction, and covariates for baseline SiSBP and the interaction between baseline SiSBP and visit. An unstructured covariance matrix will be used to account for the correlation between repeated BP measurements from the same subject.

LSM differences vs placebo at Week 4 and their 97.5% CIs will be obtained from the model. The associated p-values will be used to test the first and second null hypotheses.

### 6.2.4 Sensitivity analyses for the primary endpoint

The impact of deviations from the MAR assumption underlying the mixed model will be investigated in sensitivity analyses assuming that in the aprocitentan groups the data are MNAR [Mallinckrodt 2013].

Two control-based MI procedures will be performed under MNAR: a CR and a J2R approach [Carpenter 2013]. In addition, a tipping point approach will be used to assess how severe departures from the MAR assumption must be to overturn the conclusions of the main analysis. For details, see Section 8.2.

In another sensitivity analysis on the FAS, AOBPM measurements obtained *more than one day* after premature discontinuation of DB treatment will be excluded from the main analysis (i.e., considered as missing), leading to a hypothetical strategy estimand in ICH terminology [ICH 2017b]. This approach reflects the anticipation that the effect of a treatment on BP will be lost quickly after the treatment has been discontinued. In this setting, it is not the usual practice to assess effectiveness after (premature) treatment discontinuation [O'Neill 2012]. In addition, AOBPM measurements taken after the

---

 If the last dose of DB treatment is taken at study Day x then an AOBPM measurement taken at Day x + 1 will be included in the analysis, but a measurement taken at Day x + 2 will not.

addition of a diuretic or use of rescue medication that also has an impact on BP will be excluded from the analysis.

Finally, the primary analysis will be performed excluding site 4204 from which the data are considered not trustworthy (as per internal audit report).

### 6.2.5 Supportive analyses for the primary endpoint

As a supportive analysis, the mixed model (as specified for the main analysis) will be performed on the PPS. An ANCOVA will be performed on the FAS for the change from baseline to Week 4 imputing missing data using LOCF and, separately, using BOCF.

In LOCF a missing post-baseline value will be replaced by the preceding value (except the baseline value; so, the analysis will be restricted to subjects with a post-baseline value). In BOCF, a missing post-baseline value will be replaced by the baseline (so, the change will be zero).

### 6.2.6 Subgroup analyses for the primary endpoint

The following subgroups will be considered.

- Age at screening (18–< 65, 65–< 75 and  $\geq 75$  years).
- Sex (male/female).
- Weight at baseline ( $\leq 100$  kg,  $> 100$  kg).
- BMI at screening  $< 30$ ,  $30$ –<  $40$  and  $\geq 40$  kg/m^2.
- Race (Black or African American, White, Asian, Other\*).
- Region (Asia/Australia, Europe, North America, as defined in Section 5.4.1).
- UACR at Baseline ( $< 30$  mg/g,  $30$ – $300$  mg/g,  $> 300$  mg/g.,
- CKD stage at baseline (1–2 defined as eGFR  $\geq 60$  mL/min/1.73 m^2, 3–4 defined as eGFR  $15$  to  $< 60$  mL/min/1.73 m^2).
- Diabetes as per medical history (Y/N) (defined as Hyperglycaemia/new onset diabetes mellitus [SMQ]).
- Protocol Version 1/2 vs protocol Version 3 at randomization. Note: in protocol Version 3, beta-blockers were counted as antihypertensive medications at Screening, which was not the case in Version 1/2.

\* The 'Other' category will not be considered for subgroup analyses due to the mix of races and small number of subjects limiting the ability (i.e., low power) to detect differences between treatment groups. 'Other' includes American Indian or Alaska Native, Native Hawaiian or other Pacific Islander and Other.

If the size of a subgroup is lower than 25 subjects, subgroup categories might be pooled.

The aim of the subgroup analyses is to explore the consistency of treatment effect in relevant subgroups. Results of the subgroup analyses will be displayed in a forest plot and will include:

- An estimate of the treatment effect for each aprocitentan dose vs placebo with its 95% CI for each level of the subgroup. It will be calculated as the LSM difference vs placebo at Week 4 obtained separately for each subgroup level as described for the main analysis [Section 6.2.3] but using 95% rather than 97.5% CIs.
- A p-value for the interaction test obtained from the mixed model for the main analysis extended with factors for the subgroup, treatment by subgroup interaction and treatment by subgroup by visit interaction, with appropriate contrasts.
- A vertical reference line displayed at the level of the overall treatment effect.

The study is not designed or powered to detect interactions but an arbitrary two-sided significance level of 0.10 will be used for the interpretation of the interaction test. No multiplicity adjustment is applied as these subgroup analyses are exploratory in nature.

The analyses of the primary endpoint are summarized in [Table 4](#).

### **6.2.7 Impact of the COVID-19 pandemic on the analysis of primary endpoint**

The analysis of the primary endpoint is based on AOBPM data collected at randomization (Visit 4) and Week 4 (Visit 6). Missing data because of missed on-site Visit 4 and Visit 6 due to the COVID-19 pandemic will not be imputed but will be handled by the mixed model specified for the primary endpoint analysis.

If Visit 4 and/or Visit 6 was performed off-site and AOBPM could not be performed, HBP was to be measured instead. These values will be summarized using descriptive statistics [[D-20.063](#)] and will not be used for the analysis of primary endpoint.

## **6.3 Key secondary endpoint analysis**

### **6.3.1 Variable**

The key secondary efficacy endpoint is the change from DB-WD baseline (Week 36) to Week 40 in mean trough SiSBP measured by AOBPM.

### **6.3.2 Intercurrent events and choice of estimand**

There are three types of intercurrent events that may interfere with the analysis of the key secondary endpoint: premature discontinuation of DB-WD treatment, initiation of antihypertensive rescue medication (in the DB-WD part) or the addition / dose increase of a diuretic (in the DB-WD part).

All AOBPM measurements, irrespective of any intercurrent event(s), will be included in the analysis, leading to a treatment policy strategy estimand in ICH terminology [[ICH 2017b](#)].

It is expected that 10% of subjects in the mFAS will have a missing Week 40 AOBPM. In the main analysis [Section 6.3.3] missing data will not be imputed but will be handled by a mixed model assuming that the missing data are MAR. Sensitivity analyses will be performed, investigating the impact of deviations from MAR as well as considering a different estimand [Section 6.3.4].

### 6.3.3 Main analysis for the key secondary endpoint

The main analysis for the change from DB-WD baseline (Week 36) to Week 40 (i.e., in the DB-WD part) in mean trough SiSBP measured by AOBPM will be conducted on the mFAS. The treatment groups in this analysis are aprocitentan 25 mg and placebo. The analyses will be adjusted for the stratum at Re-randomization (i.e., randomized treatment in the DB part). The third null hypothesis ( $H_{30}$ ) will be tested as described in Section 6.1.

Changes from DB-WD baseline (Week 36) to visits up to Week 40 in mean trough SiSBP will be analyzed using a mixed model with factors for stratum (i.e., randomized treatment in the DB part), treatment group, visit, and treatment by visit interaction and covariates for DB-WD baseline (Week 36) SiSBP and the interaction between DB-WD baseline (Week 36) SiSBP and visit and an unstructured covariance matrix.

LSM differences vs placebo for the change from DB-WD baseline (Week 36) to Week 40 and their 95% CIs will be obtained from the model. The associated p-values will be used to test the third null hypothesis.

### 6.3.4 Sensitivity analyses for the key secondary endpoint

The impact of deviations from the MAR assumption underlying the mixed model will be investigated in sensitivity analyses under MNAR as described in Section 6.2.4 and detailed in Section 8.2.

In another sensitivity analysis on the mFAS, all AOBPM measurements obtained *more than one day* after premature discontinuation of DB-WD treatment will be excluded from the main analysis. In addition, the initiation of antihypertensive rescue medication could influence the BP of a subject [O'Neill 2012]. For this reason, AOBPM measurements obtained after initiation of antihypertensive rescue medication in the DB-WD part will also be excluded from this analysis (i.e., considered as missing), leading to a hypothetical strategy estimand in ICH terminology [ICH 2017b]. Finally, AOBPM measurements taken after the addition of a diuretic (but also having an impact on BP) will be excluded from the analysis. (Note: antihypertensive rescue medication or a diuretic initiated in the SB aprocitentan part that is continued unchanged in the DB-WD part will *not* lead to exclusion from analysis).

Finally, the main analysis for the key secondary endpoint will be performed excluding site 4204 from which the data are considered not trustworthy (as per internal audit report).

### 6.3.5 Supportive analyses for the key secondary endpoint

As supportive analyses, the mixed model (as specified for the main analysis) will be performed in the mPPS and ANCOVAs will be performed on the mFAS for the change from DB-WD baseline (Week 36) to Week 40 imputing missing data using LOCF and BOCF, respectively.

### 6.3.6 Subgroup analyses for the key secondary endpoint

Subgroup analyses in the DB-WD part will be performed as described for the DB part but only for age, sex, race and region [as defined in Section 6.2.6]. In addition, a subgroup analysis based on the SiSBP at DB-WD baseline ( $< 135$  mmHg vs  $\geq 135$  mmHg) will be performed. Subjects without antihypertensive rescue medication are considered an enriched sub-population of the mFAS.

The analyses of the key secondary endpoint are summarized in [Table 4](#).

### 6.3.7 Impact of the COVID-19 pandemic on the analysis of key secondary endpoint

The analysis of the key secondary endpoint is based on AOBPM data collected at re-randomization (Visit 11) and Week 40 (Visit 13). Missing data because of missed on-site Visit 11 and Visit 13 due to the COVID-19 pandemic will be handled by the mixed model specified for the key secondary endpoint analysis.

If Visit 11 and/or Visit 13 was performed off-site and AOBPM could not be performed, HBP was to be measured instead. These values will be summarized using descriptive statistics and will not be used for the analysis of the key secondary endpoint [[D-20.063](#)].

## 6.4 Other secondary efficacy endpoints analyses

### 6.4.1 Variables

The other secondary efficacy endpoints are:

- Change from baseline to Week 4 of DB treatment in mean trough SiDBP measured by AOBPM.
- Changes from baseline to Week 4 of DB treatment in 24 h mean systolic BP (SBP) and diastolic BP (DBP) measured by 24 h ABPM.
  - At each visit the 24 h mean SBP (or DBP) is derived from the area under the SBP-time (or DBP-time) curve, divided by the time span. The area under the curve is calculated by the trapezoidal rule. Time points later than 24 hours after the first time point will be excluded from the calculation. The change from baseline to Week 4 will be obtained by subtraction.
- Change from DB-WD baseline (Week 36) to Week 40 of DB-WD treatment in mean trough SiDBP measured by AOBPM.

- Changes from DB-WD baseline (Week 36) to Week 40 of DB-WD treatment in 24 h mean SBP and DBP measured by 24 h ABPM.
  - These are derived similarly to changes from baseline to Week 4 of DB treatment in 24 h mean SBP and DBP, with baseline and Week 4 replaced by DB-WD baseline (Week 36) and Week 40, respectively.

Each 24 h ABPM reading is supplemented by six quality criteria (provided by the vendor):

1. Start time must be between 06:00 and 12:00
2. Minimum duration of 24 hours after beginning of test
3. Minimum of 70% valid readings in the period
4. Total Required Hours is at least 21
5. Total Exception Hours is at most 3
6. Total Consecutive Exception Hours is 0

The main evaluation of ABPM data will be performed based on ABPMs with at least 70% valid readings and a total duration of at least 21 hours. In the calculation of the percentage, ABPM measurements performed during the first ten minutes will be counted as a single measurement to account for the manual measurements performed by the subject in testing the device. A supportive evaluation will be based on ABPM readings that satisfy all six criteria mentioned above.

#### 6.4.2 Analyses

All other secondary efficacy variables will be tested at the two-sided significance level of 0.05. No correction for multiplicity will be applied.

- *Change from baseline to Week 4 of DB treatment in mean trough SiDBP measured by AOBPM* will be analyzed in the FAS using the same mixed model as specified for SiSBP (main analysis) in the DB part.
- *Changes from baseline to Week 4 of DB treatment in 24 h mean SBP and DBP measured by ABPM* will be analyzed in the aFAS using an ANCOVA with a factor for treatment group and a covariate for baseline 24 h mean SBP (or DBP).
- *Change from DB-WD baseline (Week 36) to Week 40 of DB-WD treatment in mean trough SiDBP as measured by AOBPM* will be analyzed in the mFAS using the same mixed model as specified for SiSBP (main analysis) in the DB-WD part.
- *Changes from DB-WD baseline (Week 36) to Week 40 of DB-WD treatment in 24 h mean SBP and DBP as measured by ABPM* will be analyzed in the maFAS using the same ANCOVA as described for changes from baseline to Week 4 of DB treatment in 24 h mean SBP and DBP, but with baseline replaced by DB-WD baseline (Week 36).

The analyses of the other secondary endpoints are summarized in [Table 4](#).

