### 6.5.2 Analyses

All other efficacy variables will be tested at the two-sided significance level of 0.05. No correction for multiplicity will be applied.

- *Changes from baseline to Week 2 of DB treatment in mean trough SiSBP and SiDBP measured by AOBPM* will be analyzed using the mixed model described for changes from baseline to Week 4 in mean trough SiSBP and SiDBP, respectively.
- *Changes from baseline to Week 4 in daytime and nighttime mean SBP and DBP measured by ABPM* will be analyzed in the aFAS using the same ANCOVA as described for 24 h mean SBP and DBP.
- *Changes from DB-WD baseline (Week 36) to Week 38 of DB-WD treatment in mean trough SiSBP and SiDBP measured by AOBPM* will be analyzed in the mFAS using the mixed model described for changes from DB-WD baseline (Week 36) to Week 40 in mean trough SiSBP and SiDBP, respectively.

- *Changes from DB-WD baseline (Week 36) to Weeks 40 and 48 of DB-WD treatment in mean trough SiSBP/SiDBP measured by AOBPM will be analyzed in the mFAS using the same mixed model, extended with Week 44 and Week 48.*
- *Changes from DB-WD baseline (Week 36) to Week 40 in daytime and nighttime mean SBP and DBP measured by ABPM will be analyzed in the mFAS using the same ANCOVA as described for 24 h mean.*
- *Ratios to baseline (and DB-WD baseline [Week 36] as applicable) for all assessed time points of DB+SB and DB-WD parts in UACR will be log transformed and analyzed using a mixed model with a factor for treatment group, visit, treatment by visit interaction, covariates for baseline (DB-WD baseline [Week 36]) log UACR and visit by baseline (DB-WD baseline [Week 36]) interaction and an unstructured covariance matrix. This will be done separately for the DB+SB part on the FAS and for the DB-WD part on the mFAS.*

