- *The number (%) of subjects who discontinued study treatment due to lack of efficacy will be tabulated by study part (DB, SB aprocitentan and DB-WD) and treatment group (within study part) in the FAS (2×) and mFAS, respectively. If there are at least 12 subjects discontinued due to lack of efficacy, time from Randomization to treatment discontinuation due to lack of efficacy in the DB or SB aprocitentan part will be summarized by treatment group using Kaplan-Meier plots in the FAS. For subjects who did not discontinue treatment or discontinued treatment for reasons other than lack of efficacy, time to discontinuation will be censored at the last dose of DB or SB treatment (whichever comes last). Additionally, a ‘two-step’ Cox model with a factor for treatment will be fitted [see Section 8.2 for details]. Time from Re-randomization to treatment discontinuation due to lack of efficacy in the DB-WD part will be summarized similarly in the mSAF, except that the Cox model is the conventional one. For subjects who did not discontinue treatment or discontinued treatment for reasons other than lack of efficacy in the DB-WD part, time to discontinuation will be censored at the last DB-WD treatment + 30 days (or EOS date, whichever comes first).*
- *The number (%) of subjects who initiated antihypertensive rescue medication will be summarized by study part (SB and DB-WD; rescue medication is not allowed in the DB part) and treatment group (within study part).*
- *Home SBP/DBP collected due to the COVID-19 pandemic will be summarized by visit in DB, SB and DB-WD parts using descriptive statistics.*
- *The number (%) of subjects with SBP/DBP Control will be tabulated for the DB+SB and DB-WD parts at each visit by treatment group in the FAS and mFAS, respectively. Subjects with a missing value at a given visit will be excluded from the analysis at that visit. The Cochran-Mantel-Haenszel (CMH) test will be used to test for a difference in the Control proportions at Week 4 between treatment groups in DB part on the FAS and at Week 40 between treatment groups in DB-WD part (stratified by randomized*

treatment in the DB part) on the mFAS. The treatment effect will be expressed in terms of the aprocitentan to placebo OR and corresponding 95% CI. An OR > 1 will indicate a benefit of aprocitentan as compared to placebo.

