## 8.2 Analysis details

### 8.2.1 Mixed model for repeated measurements

This model is used, for example, for the main analyses of the primary and the key secondary endpoints.

Assuming the data are in ‘long’ format (i.e., one row for each subject/visit) example SAS® statements for the primary endpoint analysis are:

```
proc mixed data=db;
  class subjid trt01pn avisitn;
  model chg=trt01pn avisitn trt01pn*avisitn base base*avisitn/ ddfm=kr;
  repeated avisitn/ subject=subjid type=un;
  lsmeans trt01pn*avisitn/ diff=control ('3' '6') alpha=0.025;
run;
```

The data set *db* includes baseline SiSBP (*base*) as well as changes (*chg*) from baseline to Weeks 2 and 4. Furthermore, *trt01pn* equals 1, 2 and 3 for aprocitentan 12.5 mg, aprocitentan 25 mg and placebo in the DB part, respectively, and *avisitn* is 5 and 6 for Weeks 2 and 4, respectively. The Bonferroni correction [Section 6.1] will be applied by comparing the two-sided p-values vs 0.025 (rather than adding *adjust=bonf* to the *lsmeans* statement).

Again, assuming the data are in ‘long’ format example SAS® statements for the secondary endpoint analysis are:

```
proc mixed data=dbwd;
  class trt01pn subjid trt03pn avisitn;
  model chg=trt01pn trt03pn avisitn trt03pn*avisitn wk36 wk36*avisitn/
  ddfm=kr;
  repeated avisitn/ subject=subjid type=un;
  lsmeans trt03pn*avisitn/ diff=control ('5' '13') alpha =0.05(1);
run;
```

The data set *dbwd* includes DB-WD baseline (Week 36) SiSBP (*wk36*) as well as changes (*chg*) from DB-WD baseline (Week 36) to Weeks 38 and 40. Furthermore, *trt03pn* equals 4 and 5 for aprocitentan 25 mg and placebo in the DB-WD part, respectively, and *avisitn* is 12 and 13 for Weeks 38 and 40, respectively. Note that *trt01pn* (treatment in the DB part) is now used as a stratum.

 The alpha level needs to be adjusted to 0.025 in case one of H10 and H20 has been rejected.

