### 8.2.5 Control/response analysis

This analysis will be implemented by the following SAS® statement:

```
proc freq;  
  tables treatment*response / nocol nopercnt cmh1 commonriskdiff;  
run;
```

For DB-WD the analysis should be stratified by DB treatment, so treatment in DB (trt01pn) needs to be added in the tables statement.

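### The DB-WD ambulatory BP ANCOVAs and the DB-WD UACR mixed model leave out the re-randomization stratum that the key secondary model and the Week 40 CMH test include

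*SAP*

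**What the plan says.** SAP Section 6.3.3 names the stratum for the key secondary endpoint: "The analyses will be adjusted for the stratum at Re-randomization (i.e., randomized treatment in the DB part"). The code in Section 8.2.1 carries it as trt01pn: "model chg=trt01pn trt03pn avisitn trt03pn*avisitn wk36 wk36*avisitn".

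Other DB-WD analyses follow suit:

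- DB-WD diastolic office BP is analyzed "using the same mixed model as specified for SiSBP (main analysis) in the DB-WD part" (Section 6.4.2), so it inherits the stratum. The DB-WD office BP analyses in Section 6.5.2 do the same.
- The CMH test of BP control is carried out "at Week 40 between treatment groups in DB-WD part (stratified by randomized" DB treatment (Section 6.5.2). Section 8.2.5 confirms it: "For DB-WD the analysis should be stratified by DB treatment, so treatment in DB (trt01pn) needs to be added in the tables statement".

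Three sets of DB-WD analyses are specified without it:

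- **24 h ambulatory BP** (Section 6.4.2): "will be analyzed in the maFAS using the same ANCOVA as described for changes from baseline to Week 4 of DB treatment". The ANCOVA referred to is described as "using an ANCOVA with a factor for treatment group and a covariate for baseline 24 h mean SBP (or DBP"). The only stated change for the DB-WD part is the baseline.
- **Daytime and nighttime ambulatory BP** (Section 6.5.2): "will be analyzed in the mFAS using the same ANCOVA as described for 24 h mean". (Table 4 names the maFAS for these; that is a separate matter.)
- **UACR** (Section 6.5.2): the terms are treatment, visit, their interaction, log baseline UACR and its interaction with visit. The same list serves a separate DB-WD fit on the mFAS.

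Table 4 says only ANCOVA or mixed model for these rows, and Section 8.2 has no ambulatory BP or UACR code.

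**The concern.** A model for a randomized comparison should normally contain the factors by which randomization was stratified. If such a factor is prognostic and is left out, its variance stays in the residual. The treatment estimate is already balanced over the strata, so the reported standard error overstates its real uncertainty and the test becomes conservative.

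The SAP applies this principle to office BP and to the exploratory control endpoints, but not to ambulatory BP or UACR, and gives no reason. Office and ambulatory BP from the same re-randomized comparison would then be analyzed on different footings. A later wish to align them would mean choosing between adjusted and unadjusted results after the data are known.

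**Working it through.** **Terms side by side**

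| DB-WD analysis | SAP section | Stratum in model? |
|---|---|---|
| Systolic office BP, Week 40 (key secondary) | 6.3.3, 8.2.1 | Yes |
| Diastolic office BP, Week 40 | 6.4.2 | Yes, by reference |
| Office BP at other DB-WD visits | 6.5.2 | Yes, by reference |
| BP control, Week 40 (CMH) | 6.5.2, 8.2.5 | Yes |
| 24 h ambulatory BP | 6.4.2 | No |
| Daytime and nighttime ambulatory BP | 6.5.2 | No |
| UACR, DB-WD fit | 6.5.2 | No |

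The treatment factor cannot stand in for the stratum: in the mFAS and maFAS (Sections 4.1.5 and 4.1.9), subjects are grouped by their DB-WD assignment.

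**The plan's own figure.** Section 2.1 gives at least 85% power for the DB-WD part with 324 re-randomized subjects. The documents available give no effect size or SD, so it cannot be reproduced. The finding does not contradict it.

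**Inputs for the size of the effect.** Allocation is 1:1 (Section 2.1) and tests are two-sided at 0.05 (Sections 6.4.2 and 6.5.2). R² is the share of residual variance, given treatment and DB-WD baseline, that the stratum explains. It is not in the documents; 0 to 5% is assumed.

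**Formulas**, with balanced strata:

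- Ratio of reported unadjusted to adjusted SE: k = 1/√(1 − R²).
- Actual type I error of the unadjusted test: 2 × [1 − Φ(1.960k)].
- Adjusted power when the unadjusted test has 80%: Φ(0.842 + 1.960k − 1.960).

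| R² | k | Type I error, unadjusted | Adjusted power |
|---|---|---|---|
| 0% | 1.0000 | 0.0500 | 0.800 |
| 0.5% | 1.0025 | 0.0494 | 0.801 |
| 1% | 1.0050 | 0.0489 | 0.803 |
| 3% | 1.0153 | 0.0466 | 0.808 |
| 5% | 1.0260 | 0.0443 | 0.814 |

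Viewed from the other side, a test with 85% power when adjusted has 83.8% when unadjusted at R² = 5%.

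**What R² = 5% would require.** Take three equal, evenly spaced strata. The spread between the extreme strata, given baseline, is SD × √[6R²/(1 − R²)].

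- Ambulatory BP, assumed residual SD 10 to 16 mmHg: 10 × √(0.30/0.95) = 5.6 mmHg to 16 × √(0.30/0.95) = 9.0 mmHg.
- UACR, assumed residual SD of the log ratio 0.5 to 1.0: 0.281 to 0.562 on the log scale, a 1.32- to 1.75-fold difference.

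A spread of 1 mmHg gives an SE ratio of √[1 + 1/(6 × SD²)] = 1.0008 (SD 10) to 1.0003 (SD 16), so SEs are 0.08% to 0.03% too large.

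**Simulation.** 378 subjects, three strata of 126, 1:1 within stratum, baseline in both models, 20,000 runs per setting. Monte Carlo SE is about 0.0015 for type I error and 0.003 for power.

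| Setting | SE ratio | Type I error, without / with stratum | Power, without / with |
|---|---|---|---|
| R² = 0 | 1.000 | 0.051 / 0.051 | 0.797 / 0.798 |
| R² = 1% | 1.005 | 0.047 / 0.048 | 0.793 / 0.795 |
| R² = 5% | 1.026 | 0.043 / 0.048 | 0.797 / 0.811 |
| R² = 5%, 20% of subjects removed at random | 1.025 | 0.047 / 0.052 | 0.795 / 0.811 |

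The last row mimics imperfect balance in the maFAS; the 20% is assumed. The simulation agrees with the formulas.

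**The case against.** The sentence on adjusting for the stratum belongs to the key secondary main analysis. The SAP nowhere promises that every DB-WD analysis will be adjusted. A fuller model for the confirmatory endpoint beside simpler ones for endpoints outside the three tested hypotheses, without multiplicity control, is coherent. This stands: the plan breaks no commitment, and the point is one of good practice.

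Nor is harm shown. All subjects receive aprocitentan 25 mg for 32 weeks before re-randomization (Section 2.1), and DB-WD baseline is already a covariate. Nothing in the documents suggests that earlier DB treatment predicts what follows. The visible losses all sit near R² = 5%, which needs implausibly large differences between former arms. The fall to 0.044 also relies on balance within strata; with 20% of subjects removed at random, the simulated value is 0.047. All of this stands and limits the size.

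Finally, the protocol document available is only the COVID-19 addendum, so the covariates in the main protocol cannot be checked. That limits any claim about the whole plan, but does not supply the missing term in the SAP.

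What the objection does not provide is a reason for leaving out a stratification factor that the neighboring analyses contain.

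**Conclusion.** The concern holds and is minor. As written, the DB-WD 24 h, daytime and nighttime ambulatory BP ANCOVAs and the DB-WD UACR fit omit the re-randomization stratum. The DB+SB fit of the UACR model is not affected.

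The omission introduces neither bias nor type I error inflation, and the third null hypothesis is tested with a model that includes the stratum. The loss is probably negligible. Its upper end, under the assumed R² of 5%, is an SE 2.6% too large and about 1.4 percentage points of power (80.0% against 81.4%). The R² range and the residual SDs are assumptions.

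For the DB-WD tipping-point ANCOVA, the DB-WD imputation models and the LOCF and BOCF ANCOVAs (Sections 8.2.3, 8.2.2 and 6.3.5), the stratum is merely unstated. Those descriptions are brief, and the general sentence in Section 6.3.3 may cover them, so no error is claimed there. The DB-WD Cox models do not mention the stratum either and are outside this point.

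**What to change.** In SAP Sections 6.4.2 and 6.5.2, add the treatment assigned in the DB part (trt01pn) as a factor in the DB-WD 24 h, daytime and nighttime ambulatory BP ANCOVAs and in the DB-WD fit of the UACR mixed model. Otherwise, state why it is left out.

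The cost is two degrees of freedom per model. If the stratum is not prognostic, the t critical value is multiplied by about 1.00002 at both 324 and 380 subjects. The variable is already in the DB-WD data set used in Section 8.2.1.

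For consistency, when the DB-WD tipping-point, LOCF/BOCF and imputation code is written out, use trt03pn as treatment and trt01pn as the stratum. This does not mean adding treatment to the first, monotone-completing MCMC step, from which Section 8.2.2 expressly excludes it.
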